9.2.3 Concomitant Medication and Treatment

Concomitant medication prescribed for MS or other ongoing conditions during the observation period or introduced during the observation period will be documented in the electronic Case Report Form (eCRF) from start of therapy with ocrelizumab until discontinuation of the treatment, if applicable.

9.3 VARIABLES

9.3.1 Exposure Definition

Ocrelizumab-Exposed Group: Ocrelizumab exposure from 6 months prior to LMP through pregnancy will be recorded including dosing and dates of administration during each trimester of pregnancy.

Internal Comparator Group: The patient could be classified into one of the following categories based on MS treatment history:

- Pregnant women who were not exposed to any MS DMTs during the 6 months prior to their LMP or at any time during their pregnancy
- OR
- Pregnant women who were exposed to glatiramer acetate during the 6 months prior to their LMP through the first trimester

9.3.2 Outcome Variables

9.3.2.1 Primary Outcome

9.3.2.1.1 Congenital Malformations

Congenital malformations will be classified according to the EUROCAT classification system (see [Section 9.7.2.2.1](#)) and major congenital malformations will serve as the primary outcome in this study. The remaining outcomes described in [Section 9.3.2](#) will be designated as secondary outcomes. All potential congenital malformations will be evaluated by a qualified, independent teratologist using all available medical records. The classification of potential congenital malformations will be based upon the teratologist's adjudication. The exact grouping of congenital malformations will mirror classification systems used in the external comparator groups.

Major congenital malformations identified up to 1 year of age by the mother or by the HCP or identified in the dysmorphological examination will be included in the primary analysis. Any defects identified after 1 year of age will be included if available, and descriptive analysis on these defects will be provided. More details will be provided in the Statistical Analysis Plan (SAP).

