 - Pregnancy outcome, if applicable (e.g., elective or therapeutic termination, spontaneous abortion, ectopic pregnancy, molar pregnancy) as per [Section 9.3.2](#)

- Reason for elective or therapeutic termination (e.g., prenatal testing finding, risk to mother's health, undesired pregnancy), if applicable
 - Autopsy results and pathology reports, if available
- Changes in MS disease status (including treatment changes and relapses, EDSS score)
- Ocrelizumab treatment (including start and stop dates, dose, dosing frequency, reason for discontinuation [if applicable])
- Changes in comorbid conditions
- Current lifestyle factors (e.g., smoking, caffeine consumption, alcohol use, illicit drug use)
- Current medications (including other MS treatments such as glatiramer acetate, teratogenic medications or medication with potential fetal health implications, corticosteroids, folic acid, other vitamins and supplements, vaccinations, medications to treat other chronic diseases)
- SAEs related to pregnancy (as per [Section 11](#))

Birth outcome follow-up (approximately 4 weeks after EDD):

- Date of contact and date of pregnancy outcome or gestational age (in weeks)
- Changes in contact information; contact information for infant's HCP
- Reporter of information (patient, obstetrician, infant HCP)
- Pregnancy outcome (as per [Section 9.3.2](#), e.g., live birth, stillbirth, spontaneous abortion, elective or therapeutic termination):
 - Reason for elective or therapeutic termination (e.g., prenatal testing finding, risk to mother's health, undesired pregnancy), if applicable
 - Autopsy results and pathology reports, if available
- Mode of birth (vaginal delivery, assisted delivery/cesarean section, type of anesthesia)
- MS disease and treatment status since last follow-up
- Ocrelizumab treatment (including start and stop dates, dose, dosing frequency, reason for discontinuation [if applicable])
- Changes in comorbid conditions
- Current lifestyle factors (e.g., smoking, caffeine consumption, alcohol use, illicit drug use)
- Current medications (including other MS treatments such as glatiramer acetate, teratogenic medications or medication with potential fetal health implications, corticosteroids, folic acid, other vitamins and supplements, vaccinations, medications to treat other chronic diseases)

- Infant characteristics:
 - Gestational age at birth
 - Sex
 - Weight
 - Length
 - Head circumference
 - Birth order (for multiple births), and number of fetuses

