9.7.2 Comparative Analyses

Congenital malformation reporting rates, spontaneous abortion rates, and preterm birth rates from the study will be compared with the internal comparator group and other available background rates from external comparator populations including, but not limited to: EUROCAT, MACDP, and the Roche Multi-Source Surveillance Study of Pregnancy and Infant Outcomes in Ocrelizumab-Exposed Women with MS (protocol number: BA39732). These comparisons will be based on examination of point estimates and 95% CIs from each of the sources and in order to facilitate comparisons, details regarding the coding classification and case definition will be made as similar as possible. Details about how to set coding and classification of each event comparable to each external data source will be described in the SAP.

For the internal comparison group, methods such as causal inference models using baseline characteristics will be outlined in the SAP. The comparison of the internal comparator to ocrelizumab-exposed women will be performed using risk ratios (95% CIs) unadjusted and adjusted to relevant covariates, if sufficient number of outcomes are available.

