9.7.2.1 Internal Comparator Group

The internal comparator group will consist of pregnant women with MS who are unexposed to DMTs, apart from glatiramer acetate (See [Section 9.2.2.2](#)). Identical data collection and follow-up procedures will be used for the ocrelizumab-exposed pregnant women and unexposed pregnant women with MS. Covariates collected in both exposed and unexposed groups include the following: pregnancy follow-up and frequency of mother and infant encounters, medical and medication history, MS disease history and relapses during follow-up, and pregnancy and infant outcomes (see [Appendix 2](#) and [3](#)). This comparator study population will be recruited from the same clinical centers as the ocrelizumab-exposed pregnant women, in both the United States and other countries.

There is sufficient clinical evidence to allow pregnant women with MS who are exposed to glatiramer acetate early in pregnancy to enroll in the internal comparator. Since FDA drug approval in 1996, studies of glatiramer acetate have not shown to increase the risk of adverse pregnancy or delivery outcomes compared to women unexposed to DMTs during pregnancy ([Copaxone \[Teva\] Prescribing Information](#); [Fragoso 2014](#); [Sandberg-Wollheim et al. 2018](#)), including in the first trimester ([Herbstritt et al. 2016](#)); thus, exposure to this particular MS DMT will be permitted as part of the ocrelizumab-unexposed group to increase the feasibility to recruit an internal comparator group from the same sites. However, analyses stratification based on glatiramer acetate exposure will also be performed.

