9.8.4 Administrative Structure

9.8.4.1 External Advisors

A qualified independent teratologist or other appropriate birth defect expert will be used throughout the study for evaluation of congenital malformations and other significant findings. Other experts in relevant specialties will also be consulted by the Sponsor as deemed necessary by the external advisors.

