11.1.1.1 Assessment of Serious Adverse Events (Immediately Reportable to the Roche)

Serious Adverse Events

Only pregnancy-related SAEs, pregnancy outcomes, and infant SAEs will be collected in this study.

An SAE is any untoward medical occurrence that:

- Is fatal (i.e., the AE actually causes or leads to death)
- Is life-threatening (NOTE: The term “life-threatening” refers to an event in which the patient was at immediate risk of death at the time of the event; it does not refer to an event that hypothetically might have caused death if it was more severe)
- Requires or prolongs inpatient hospitalization
- Results in persistent or significant disability/incapacity (i.e., the AE results in substantial disruption of the patient’s ability to conduct normal life functions)
- Is a significant medical event in the physician’s judgment (e.g., may jeopardize the patient or may require medical/surgical intervention to prevent one of the outcomes listed above)

Obstetric complications that fall into the above categories are defined as pregnancy-related SAEs in this study and should be reported to the CC.

A pregnancy outcome is as outlined in [Section 9.3](#), Outcome Variables, and covers:

- Spontaneous abortion
- Fetal loss including stillbirth
- Ectopic pregnancy
- Molar pregnancy
- Congenital malformation
- Elective or therapeutic pregnancy terminations
- Premature birth

The reporting HCP must assess the relationship to the studied medicinal product and severity for each SAE recorded on the eCRF (see [Appendix 4](#)).

The terms “severe” and “serious” are not synonymous. Severity refers to the intensity of an AE (e.g., rated as mild, moderate, or severe, or according to the NCI CTCAE; see [Appendix 4](#)).

Normal delivery and elective cesarean sections performed for non-medical reasons (i.e., scheduling, personal preference) and their related hospitalizations will not be considered pregnancy-related SAEs, unless, in the view of the reporting physician, the hospitalization was prolonged due to a complication.

Non-Serious Adverse Events

In neonates and infants, the following non-serious AEs will be collected during their first year of life: severe infections of NCI CTCAE severity Grade 3, neutropenia, lymphopenia, leukopenia, thrombocytopenia, decreased B-cell counts, hypogammaglobulinemia, and

inadequate vaccine response, including low vaccine-induced response titers (for laboratory test results see also [Appendix 4.3.3](#)).

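### The primary outcome is adjudicated from all available records with no rule masking exposure, so borderline major/minor calls are open to exposure-aware judgement

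*Protocol*

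**What the plan says.** Protocol section 9.3.2.1.1 names major congenital malformation as the primary outcome. On how a case is decided it says "All potential congenital malformations will be evaluated by a qualified, independent teratologist using all available medical records", and then "The classification of potential congenital malformations will be based upon" that person's adjudication. The framework is the EUROCAT classification, with grouping aligned to the external comparators.

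The role appears again in section 9.8.4.1: "A qualified independent teratologist or other appropriate birth defect expert will be used throughout the study". There, too, the expert is described as independent, and nothing is said about what the expert may or may not see.

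The adjudicated outcome feeds two comparisons. Section 9.5 sets the exposed-group prevalence against a 3% external baseline. Section 9.7.2 adds the two-group comparison: "The comparison of the internal comparator to ocrelizumab-exposed women will be performed using risk ratios (95% CIs) unadjusted and adjusted". Section 9.5 calls the internal comparison supportive. Section 9.7.2.1 promises equal handling of the groups in these terms: "Identical data collection and follow-up procedures will be used for the ocrelizumab-exposed pregnant women and unexposed pregnant women with MS". Adjudication is not mentioned there.

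**The concern.** Independence describes the teratologist's affiliation. It does not hide which group a mother belongs to. A rule that supplies every available record and excludes nothing leaves exposure in view unless someone removes it, and no one is told to.

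Most malformations will be classified the same way whoever looks. The exposure-sensitive part is the borderline finding that could be called major or minor. If such findings are graded even slightly differently when ocrelizumab is known to be involved, the exposed-group prevalence shifts. So does the risk ratio against the internal comparator, where exposure is known to be absent. The direction cannot be foretold: suspicion of the drug could raise grades, and reluctance to attribute harm to it could lower them. With only a handful of events expected, one or two such calls are enough to matter.

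**Working it through.** **Is exposure likely to be visible?** The relevant places, side by side:

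- Sections 9.3.2.1.1 and 9.8.4.1: all available medical records, independent expert, no masking or redaction.
- Section 9.3.2.3, birth outcome contact: ocrelizumab dates, dose and frequency are collected at the same contact as any malformation, and the malformation entry itself includes attribution.
- Section 11.1.1.1: "The reporting HCP must assess the relationship to the studied medicinal product and severity for each SAE recorded on the eCRF". Congenital malformation is on that section's list of pregnancy outcomes.
- Appendix 3, Tables 3 and 4: infant event entries carry fields for relationship to ocrelizumab and to glatiramer acetate.
- Section 9.9: the limitations cover early losses, loss to follow-up, differential recall and channeling. Exposure-aware classification of the outcome is absent.
- ENCePP checklist (Appendix 1): item 7.2.2, which covers endpoint misclassification, is ticked with a reference to 9.9; item 6.3, on validity of outcome measurement, refers to 9.6.1, which is data management. Neither section deals with adjudication.

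Exposure is therefore recorded next to the outcome, and nothing takes it out before review.

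**The plan's own size.** Inputs from section 9.5 and Table 2: p0 = 0.03, relative risk 2.5 so p1 = 0.075, two-sided α = 0.05, power 80%, drop-out 15%, live birth rate 62%.

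- n = [(1.960·√(0.03·0.97) + 0.842·√(0.075·0.925)) / 0.045]² = 152.7, so 153 outcomes.
- Enrolment = 153 / (0.62·0.85) = 290.3, so 290.

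Both stated figures reproduce. Expected cases at the 3% baseline: 0.03·153 = 4.6.

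**What one call does to the prevalence.**

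- 1/153 = 0.65 percentage points.
- Clopper-Pearson lower limit, the 2.5% quantile of Beta(x, 153 − x + 1): x = 10 gives 3.18%; x = 9 gives 2.72%.

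The 3% baseline lies between the two. Table 3 prints 2.8% for 9 cases; that value is obtained from 6% of 153 = 9.18 rather than from 9. It also fails to exclude 3%, so the reading is the same.

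**What one call does to the internal risk ratio.** Assume equal denominators, so that the ratio is a/b with a exposed and b comparator cases.

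- One exposed case reclassified: relative change 1/a. With a = 10 this is 10%; going from 9 to 10 it is 11%; with a = 5 it is 20%.
- One comparator case reclassified at b = 5 (close to the 4.6 expected if the comparator also yields 153 outcomes at 3%): 5 to 6 multiplies the ratio by 5/6 = 0.83 (−17%); 5 to 4 multiplies it by 5/4 = 1.25 (+25%).

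**Illustration of systematic shifts.** The shift sizes below are assumptions, not figures from the protocol. X is binomial with n = 153, and 10 cases is the smallest count whose exact interval excludes 3%.

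- No true effect (p = 0.03): P(X ≥ 10) = 1.8%. If exactly one borderline finding is upgraded, 9 true cases suffice: P(X ≥ 9) = 4.2%. If two are upgraded, P(X ≥ 8) = 9.1%.
- True relative risk 2.5 (p = 0.075): P(X ≥ 10) = 71.8%. If 10% of exposed cases are called not major (p = 0.0675), 58.8%. If 20% (p = 0.06), 43.7%.

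**The case against.** The strongest reply is that the point rests on silence. Section 9.3.2.1.1 does not say the teratologist is unmasked, does not list what is sent, and defers further detail to the SAP; packet preparation often sits in a SAP or an adjudication charter. The treatment and causality fields are registry entries, and no section says they are part of the medical records reviewed. The reference to all available records can be read as a completeness rule that still permits redaction.

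This stands in part. That the teratologist will see exposure is an inference, and a reader who concludes that the protocol sends exposure data to the teratologist goes beyond the text. But the protocol fixes the source as all available records with nothing withheld. Masking is also a rule of conduct that has to be in place before the first case is reviewed, and interim analyses are annual.

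Three further replies also stand in part:

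- EUROCAT classification, one adjudicating role for all cases, and identical data collection confine discretion to borderline findings. The protocol gives no count of these.
- The internal comparison is only supportive, and Table 2 asks for 418 outcomes to power it at a relative risk of 2.5. The synopsis also says no inductive inference will be drawn from the external comparisons, although section 9.5 speaks of rejecting a relative risk of 1. The prevalence and its interval nevertheless remain the main result, and exposed cases feed both.
- Records are kept at least 15 years (section 9.8.3), so a masked re-review is possible. A reader might infer that the bias could never be corrected afterwards; that is too strong. Re-review could repair it in part, at more cost than masking at the outset.

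**Conclusion.** The point holds as a weakness of the stated method, to be fixed before adjudication starts; it is not an error of arithmetic, and the sample size is unaffected. The primary outcome rests on one role's adjudication from unrestricted records, exposure is probably visible, and no rule hides it.

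The single-case figures in the check show how much a single borderline call can weigh. They do not measure a bias, and it would be wrong to read them as evidence that classification will be biased or in which direction. They assume 153 evaluable births; the risk-ratio figures also assume equal denominators and, for the comparator, about 5 cases.

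**What to change.** Add to section 9.3.2.1.1:

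- Before review, the coordinating centre removes study group, all MS treatment, and any attribution or causality assessment by a healthcare provider from each suspected-case packet, in the same way for both groups.
- The teratologist classifies without knowledge of exposure, and that classification is the one used in the primary analysis.
- Any later unmasked review is recorded and reported separately.

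Section 9.8.4.1 should refer to the same rule, and section 9.9 should name the residual risk.

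The cost is redaction work on suspected cases only, with no extra assessor. Masking may be incomplete where exposure appears in narrative text such as discharge letters.

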9.3.2.2 Secondary Outcomes

9.3.2.2.1 Elective or Therapeutic Pregnancy Terminations

Elective or therapeutic pregnancy terminations are defined as any induced or voluntary fetal loss during pregnancy. If available, data from pathologic examination of the abortus or fetus will be evaluated for structural and chromosomal defects. The reason for elective or therapeutic termination will be collected.

9.3.2.2.2 Spontaneous Abortions

A spontaneous abortion is defined as loss of a fetus due to natural causes at <20 weeks of gestation. If available, information from gross or pathologic examination of the abortus or fetus will be evaluated for structural and chromosomal defects.

9.3.2.2.3 Fetal Death or Stillbirth

Fetal death or stillbirth refers to the death of a fetus prior to birth or after 20 weeks of gestation. In the event of a stillbirth or fetal death, full pathology details will be requested and examined for structural or chromosomal defects. The final classification between fetal death/stillbirth and spontaneous abortion will be based on gestational age.

9.3.2.2.4 Live Birth

A live birth refers to a complete expulsion or extraction from its mother of a surviving neonate.

9.3.2.2.5 Preterm Birth

A live birth will be classified as preterm prior to 37 weeks of gestation (www.cdc.gov). Early preterm (<34 weeks), late preterm (34–36 weeks), early term (37–38 weeks) are additional stratifications that may be considered during the analysis and will be outlined in the SAP.

9.3.2.2.6 Size for Gestational Age

All live births will be classified as small, appropriate, or large for gestational age using the Centers for Disease Control and Prevention (CDC) definition (www.cdc.gov) of birth weight below the 10th percentile, between the 10th and 90th, and above the 90th percentile for age, respectively.

9.3.2.2.7 Low Birth Weight

An infant with low birth weight will be classified as weighing under 2500 g (www.cdc.gov). Very low birth weight are infants who weigh <1500 g and moderate birth weight ranges between 1500–2499 g; these are additional stratifications that may be considered during the analysis and will be outlined in the SAP.

9.3.2.2.8 Ectopic Pregnancies

Any reported ectopic pregnancy will be sub-classified in the respective pregnancy outcome, including induced termination, maternal death, or spontaneous pregnancy loss.

9.3.2.2.9 Molar Pregnancies

Any reported molar pregnancy will be sub-classified in the respective pregnancy outcome, including induced termination, maternal death, or spontaneous pregnancy loss.

9.3.2.2.10 Serious and Severe Infections and Hospitalization of Infants

A serious infection will be defined as any infection in the infant that fulfills the definition of an SAE outlined in [Section 11.1.1.1](#). Any infant hospitalization, other than for a standard post-birth hospital stay, and severe infections of National Cancer Institute Common

Terminology Criteria for Adverse Events (NCI CTCAE) severity Grade 3, will also be captured as a secondary outcome in addition to an SAE.

9.3.2.2.11 Adverse Infant and Childhood Outcomes Related to Immune Suppression

Adverse infant and childhood outcomes related to immune suppression include neutropenia, lymphopenia, leukopenia, decreased B-cell counts, hypogammaglobulinemia, inadequate vaccine response, and events related to a potential immune mediated mechanism, including thrombocytopenia.

9.3.2.2.12 Neonatal Death

A neonatal death is defined as a death occurring in a neonate prior to 28 days of life. In the event of a neonatal death, full pathological details will be requested, and any structural or congenital defects detected will be evaluated.

9.3.2.2.13 Perinatal Death

Perinatal death is defined as the death of an infant between 28 days of life and 12 weeks of life. In the event of a perinatal death, full pathological details will be requested, and any structural or congenital defects will be evaluated.

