2017, there were 25 pregnancies reported during ocrelizumab trials in MS. Seven of the 25 pregnancies were electively terminated, and no abnormalities were reported in the embryos or products of conception, one pregnancy ended in stillbirth at approximately 7-8 months of gestation, and there were two live preterm births with abnormal findings (benign nasopharyngeal neoplasm, jaundice, respiratory distress and low birth weight; temperature instability feeding difficulties, bradycardia, respiratory distress, and anemia). Eleven of the 25 pregnancies ended in a live, full-term birth and 4 pregnancies were still ongoing at the time of analysis (Vukusic et al. 2017). In an embryo-fetal development study in cynomolgus monkeys, there was no evidence of teratogenicity or embryotoxicity (Study 04-1272-1342). Also in monkeys, using doses similar to or larger than those used clinically on a mg/kg basis, increased perinatal mortality (in some cases associated with bacterial infections), depletion of circulating B cells, and toxicity to kidneys (glomerulopathy and inflammation), bone marrow (lymphoid follicle formation), and testis (reduced weight) were seen in the offspring in the absence of toxicity in the mother (Genentech Inc. 2017). Transient peripheral B-cell depletion and lymphocytopenia have been reported in infants of women treated during pregnancy with other drugs with the same mechanism of action. Due to the potential depletion of B-cells in neonates and infants of mothers who have been exposed to OCREVUS during pregnancy, it is recommended that vaccination with live or live-attenuated vaccines should be delayed until B-cell levels have recovered; therefore, measuring CD19-positive B-cell level, in neonates and infants, prior to vaccination is recommended. It is recommended that all vaccinations other than live or live-attenuated should follow the local immunization schedule. Measurement of vaccine-induced response titers should be considered to check whether individuals can mount a protective immune response, because the efficacy of the vaccination may be decreased (study BN29739, unpublished results). Ocrelizumab was excreted in the milk of treated monkeys. The effects on the infant of ocrelizumab exposure through lactation are not known (Genentech Inc. 2017).

The Ocrelizumab Pregnancy Registry will be conducted to fulfill part of the FDA postmarketing requirements (PMR) (3194-3) for approval of ocrelizumab in the United States.

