9.3.2.2.14 Infant Death

Infant death is defined as the death of an infant occurring between 12 and 52 weeks of life. In the event of an infant death, full pathological details will be requested, and any structural or congenital defects will be evaluated.

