9.3.2.2.15 Maternal Death

Maternal death is defined as the death of a pregnant woman during pregnancy, labor, or delivery. Maternal deaths for up to 12 weeks after delivery will also be reported and full pathology details will be requested.

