If the patient experiences an adverse pregnancy outcome or has an elective or therapeutic termination or a termination of unknown cause, the HCP and patient will be encouraged to report the outcome to the CC as soon as possible. In the event of an elective or therapeutic termination, spontaneous abortion, fetal death or stillbirth, communications with the patients will cease after pregnancy outcome information has been obtained.

See [Figure 1](#) for data collection overview.

Figure 1 Data Collection Overview

See [Appendix 2](#) for the data collection overview (as per standard of care) during the treatment period.

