11.1.2 Methods and Timing for Capturing and Assessing Safety Parameters

The CC is responsible for ensuring that all SAEs related to pregnancy, pregnancy outcomes, and infants, as well as the following non-serious AEs during the neonate’s/infant’s first year of life: severe infections of NCI CTCAE severity Grade 3, neutropenia, lymphopenia, leukopenia, thrombocytopenia, decreased B-cell counts, hypogammaglobulinemia, and inadequate vaccine response, including low vaccine-induced response titers, are reported by HCPs as per protocol (see [Section 11.1.1.1](#) for definition) and are recorded in the eCRF.

Once the patient is enrolled in the study, SAEs related to pregnancy will be collected until the end of her observation period, i.e. until a pregnancy outcome is reported, unless the patient withdraws from the study prematurely. SAEs and the selected non-serious AEs described above experienced by the infant will be reported until the first year of life.

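### Perinatal death is defined as death from 28 days to 12 weeks and infant death as 12 to 52 weeks, so both mortality outcomes are mislabelled; separately, the collection period for maternal death is contradictory

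*Protocol*

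**What the plan says.** The protocol lists these deaths as separate secondary outcomes:

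- Section 9.3.2.2.3: "Fetal death or stillbirth refers to the death of a fetus prior to birth or after 20 weeks of gestation". The split from spontaneous abortion rests on gestational age.
- Section 9.3.2.2.12: "A neonatal death is defined as a death occurring in a neonate prior to 28 days of life".
- Section 9.3.2.2.13: "Perinatal death is defined as the death of an infant between 28 days of life and 12 weeks of life".
- Section 9.3.2.2.14: "Infant death is defined as the death of an infant occurring between 12 and 52 weeks of life".

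The background (section 7.2) reports "increased perinatal mortality (in some cases associated with bacterial infections") among the findings in offspring of exposed monkeys. It also uses perinatal mortality in its summary of the literature on MS pregnancies.

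On the mother, section 9.3.2.2.15 says: "Maternal deaths for up to 12 weeks after delivery will also be reported". Section 11.1.2 collects pregnancy-related SAEs only "until a pregnancy outcome is reported, unless the patient withdraws from the study prematurely". After a termination, spontaneous abortion, fetal death or stillbirth, section 9.4.2 says that "communications with the patients will cease after pregnancy outcome information has been obtained".

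**The concern.** Perinatal means around birth. A window that starts on day 28 holds none of the deaths that the word denotes. Infant death, read normally, covers the whole first year of a live-born child, but here it omits the first 12 weeks. A reader of the registry report who looks for the perinatal signal from section 7.2 would go to the perinatal death line and find only post-neonatal deaths. A reader who sets either rate beside a published rate of the same name would be comparing different quantities.

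The maternal issue is separate. The definition promises 12 weeks of ascertainment, while the section that fixes the collection period stops earlier. Unless this is settled, centers may apply different end dates, and a zero count of late maternal deaths could not be interpreted.

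**Working it through.** No sample size, power or error rate depends on these definitions, so there is no stated figure to reproduce. The check is of windows and of collection routes.

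**1. Windows in days of life**

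| Outcome | Section | Days | Length |
|---|---|---|---|
| Stillbirth | 9.3.2.2.3 | before birth | – |
| Neonatal death | 9.3.2.2.12 | 0 to 28 | 28 |
| Perinatal death, as defined | 9.3.2.2.13 | 28 to 84 (12 × 7) | 56 |
| Infant death, as defined | 9.3.2.2.14 | 84 to 364 (52 × 7) | 280 |

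The sum is 28 + 56 + 280 = 364 days. There is no gap, and the only shared point is the 12-week boundary.

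**2. Where individual deaths fall**

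- Stillbirth: counted as stillbirth, not as perinatal death.
- Death on day 3: counted as neonatal, not as perinatal or infant death.
- Death at 10 weeks (day 70): counted as perinatal, not as infant death.

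The labels are therefore wrong, but every death has a category.

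**3. Comparability**

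Section 9.7.2.2.1 gives mortality for a European cohort in three bands: stillbirth, within 7 days, and days 7 to 27. All three end before day 28, so none overlaps the registry's perinatal or infant window. A comparison with those bands would have to use the registry's stillbirth and neonatal outcomes.

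**4. Maternal death**

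| Section | What it implies |
|---|---|
| 9.3.2.2.15 | deaths reported to 12 weeks after delivery |
| 11.1.2 | maternal pregnancy-related SAE collection ends at the reported outcome |
| 9.4.2 | patient contact ends after a loss, including stillbirth; patient contacts at 12, 26 and 52 weeks are for live births only |
| 11.1.2.1 | pregnancy-related SAEs sought at every patient and HCP contact; no end date given |
| Appendix 2 | combined SAE row marked at pediatric follow-up, with a footnote extending it through the study |
| 9.3.2.3 and Appendix 3 Table 4 | pediatric follow-up lists hold infant SAEs only |
| Appendix 4.3.5 | all deaths in the SAE reporting period recorded, by reference to 11.1.2.1 |

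After a live birth there is a 12-week contact, but its data lists have no maternal item. After a stillbirth, patient contact ends. Section 9.4.2 also lists a contact with the patient's HCP 4 weeks after the expected delivery date, about gestational week 44, and does not restrict it to live births. Since 44 − 32 = 12, that contact comes at least 12 weeks after a loss at or before week 32. After a stillbirth at week 38 it comes 44 − 38 = 6 weeks later, leaving weeks 6 to 12 without a planned contact. The protocol does not say whether this HCP contact goes ahead after a loss.

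**The case against.** The strongest reply is that this is only a label. Stillbirth and neonatal death are outcomes in their own right, with pathology requested, so a rise in deaths around birth would appear in two adjacent rows. The internal comparator has identical data collection and follow-up (section 9.7.2.1), so that contrast is not distorted. Section 9.7.2 names malformations, spontaneous abortion and preterm birth for external comparison, and the synopsis adds other events only where data are available. No background rate called perinatal or infant mortality is quoted. All of this stands, and it limits the point to naming and comparability.

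Some stronger readings are tempting but not supported:

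- A reader might infer that the registry's mortality would fall far below any comparator. The internal comparator uses the same definitions, and the external figures quoted are in other bands.
- A reader might add 2.33% and 2.37% from section 9.7.2.2.1 and take 4.70% as the mortality missed. The reference list shows that cohort to be pregnancies complicated by major congenital anomalies, and a common denominator is not clearly stated. Section 9.7.2.2.2 gives population stillbirth of 7.6 to 8.0 per 1,000.
- A reader might take perinatal mortality as the only offspring signal from animals. Section 7.2 also lists B-cell depletion and kidney, bone marrow and testis findings.
- A reader might infer that maternal deaths cannot be collected at all, or that 38% of women (100% − 62% live births) have no route. Live births have a partial route. The 38% includes spontaneous abortions and terminations, whereas section 9.3.2.2.15 speaks of delivery.

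**Conclusion.** The point holds as a defect of definition in two named secondary safety outcomes. The perinatal window contains no stillbirth and no death before day 28, and the infant window omits the first 84 days. This is true under any usual meaning of perinatal, so it does not depend on a particular gestational cut-off. No infant death is lost, and conventional rates can be rebuilt, assuming that dates of birth and death are recorded as planned.

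The maternal point holds in a narrower form. The sections contradict each other on when collection ends, and the clearest gap follows a late stillbirth. The documents give no basis for estimating how many maternal deaths this would affect.

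**What to change.** - Define perinatal death as stillbirth plus death within 7 days of birth, the early-neonatal cut-off already used in section 9.7.2.2.1. State the gestational cut-off for stillbirth beside it.
- Define infant death as any death of a live-born infant before 52 weeks.
- Keep 28 days to 12 weeks and 12 to 52 weeks as named sub-periods. Note in the tables that the redefined outcomes overlap stillbirth and neonatal death, so the rows must not be summed.
- Reconcile sections 9.3.2.2.15, 9.3.2.3, 9.4.2, 11.1.2, 11.1.2.1, Appendix 2, Appendix 3 Table 4 and Appendix 4.3.5, so that maternal death is ascertained over the stated 12 weeks. One way is a maternal status item at the existing 12-week contact. State also how it is ascertained after a stillbirth.

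The definitions cost only wording, since the dates are already to be collected. The maternal change costs one form item for live births and a stated procedure, possibly one further contact, after a stillbirth.
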